APPENDIX I: Treatment Settings

APPENDIX II: Example Informed Consent Form

APPENDIX III: Proposed QA Monitoring Guidelines and Check List

APPENDIX IV: Instructions For Evaluating And Reporting Adverse Events

APPENDIX V: Clonidine References

1.0 LIST OF ABBREVIATIONS

Abbreviation Definition

AE adverse event

AIDS acquired immune deficiency syndrome

ALP alkaline phosphatase ALT/SGPT alanine aminotransferase

ARSW Adjective Rating Scale for Withdrawal

ASI Addiction Severity Index AST/SGOT aspartate aminotransferase BUN blood urea nitrogen

CLIA Clinical Laboratory Improvement Amendment of 1988

COWS Clinical Opiate Withdrawal Scale

CRF Case Report Form CPK creatine phosphokinase

CSQ Client Satisfaction Questionnaire CTN NIDA Clinical Trial Network

DSM-IV Diagnostic and Statistical Manual of Mental Disorders Fourth Edition

ECG electrocardiogram

GGT gamma glutamyltranspeptidase HIV human immunodeficiency virus

LAAM levomethadyl acetate (L-alpha acetylmethadol)

LDH Lactic dehydrogenase

[figure not shown]
NIDA National Institute on Drug Abuse

SAE serious adverse event

DSM-IV checklist for substance dependence and abuse disorders

SDR study discharge report VAS Visual Analog Scales

2.0 STUDY SCHEMA

3.0 PROTOCOL SYNOPSIS

STUDY OBJECTIVES: To assess the relative clinical utility of buprenorphine-naloxone (BUP/NX) in comparison to clonidine for short term opiate detoxification initiated in the in-patient setting. It is hypothesized that BUP/NX detoxification will be more effective in sustaining treatment retention and abstinence, reducing the frequency of ancillary medications dispensed, and alleviating withdrawal symptoms than clonidine detoxification.

STUDY DESIGN: This is a randomized, open-label, parallel-group design study in which, after screening and baseline assessments are performed, patients will be randomly assigned, in a 2:1 ratio to either a BUP/NX or clonidine 13 day detoxification regimen, respectively. The standard counseling procedures used at each clinic, along with self-help detoxification handbooks, will be offered to all patients on the study. After the 13-day detoxification period, patients will be assessed for relapse, withdrawal symptoms, and treatment satisfaction at follow-up visits occurring 1, 3, and 6 months after starting detoxification.

STUDY POPULATION: Three hundred sixty (360) patients meeting Diagnostic and Statistical Manual of Mental Disorders Fourth Edition (DSM-IV) criteria for opiate dependence determined by DSM-IV checklist who are seeking treatment, and report experiencing symptoms of opiate withdrawal, are currently physically dependent on opioids, and are in need of medical assistance for opioid withdrawal, will be randomized into one of two treatment groups (240 in the BUP/NX group and 120 in the clonidine group).

ELIGIBILITY CRITERIA: Treatment seeking males and females, at least 15 years-of-age, with a DSM-IV diagnosis of opiate dependence with the ability to understand and provide written informed consent will be included. Women of childbearing capacity will be required to use an acceptable method of birth control.

Patients will be excluded if they have any medical condition that would make participation medically hazardous, have clinically significant abnormalities in ECG, have known allergy or sensitivity to buprenorphine, naloxone, or clonidine, or have acute severe psychiatric condition, or immediate suicide risk. Patients who are dependent upon alcohol, benzodiazepines, or other depressants or stimulants, requiring immediate medical attention or who have participated in another investigational study within the last 30 days will be excluded. Patients receiving beta-blockers, calcium channel blockers, tricyclics, digitalis and other medication which may interact adversely with clonidine, and patients who have had methadone or LAAM maintenance or detoxification within 30 days of enrollment will also be excluded. Patients who have pending legal actions or for any reason are unable to remain in the area for the duration of the active phase of treatment will be excluded.

STUDY INTERVENTIONS: Patients randomized to the BUP/NX arm will receive daily doses for 13 days with sublingual administration of 2 mg buprenorphine -0.5 mg naloxone tablet(s) and/or an 8 mg buprenorphine – 2.0 mg naloxone tablet(s). The starting dose on day 1 is 4 mg/1 mg BUP/NX with an additional 4 mg/1 mg, if needed, escalating in a step-wise manner to 16 mg/4 mg BUP/NX on day 3 and tapering to 2 mg/ 0.5 mg BUP/NX by days 12 to 13. Patients randomized to the clonidine arm will receive oral clonidine (0.05 to 0.1 mg depending upon weight) every 4 to 6 hours for 24 hours not to exceed 0.6 mg total on day 1 and, assuming oral clonidine is well tolerated, a clonidine transdermal patch will be applied (0.1 mg/day/7-day patch with number of patches adjusted by weight). Oral clonidine will continue to be given on the second day of detoxification and increased to 0.2 mg every 6 hours or 0.1 mg every 3 hours not to exceed 0.8 mg over 24 hours. Patches will be worn for up to 13 days of detoxification. The dose of clonidine will be adjusted according to the proposed detoxification schedule, patient's weight, tolerance, and systolic blood pressure. Patients will receive counseling according to procedures in existence at each CTP throughout the study. Self-help detoxification handbooks will be distributed to all study participants.

DURATION OF THE STUDY: The total duration of study participation for each patient will be a maximum of 6 months consisting of: screening and baseline assessments; detoxification (13 days); and, follow-up evaluations conducted at 1, 3, and 6 months after enrollment. It is estimated that 2 patients will be enrolled per site per week with a total of 6 sites. Thus, the estimated length of enrollment is 30 weeks.

SAFETY ASSESSMENTS: Before any study procedures are performed, patients will be required to provide signed informed consent. All candidates for study enrollment will have a physical examination including vital signs and weight, medical history and history of prior medication use assessment, and psychiatric evaluation (ASI Lite) including a DSM-IV checklist for substance dependence, HIV risk assessment, and clinical laboratory studies (blood chemistry, hematology, Hepatitis B and C serology, and urinalysis) performed during screening/ baseline. All patients will have a 12-lead electrocardiograph (ECG). Females will be given a pregnancy test. Assessments of adverse events (AEs) and concomitant medication use will be performed daily during detoxification and at the one-month visit. Serious Adverse Events (SAEs) will be reported during the treatment and follow-up phases of the study.

OUTCOME ASSESSMENTS: Abstinence from opiates, amphetamines, cocaine, cannabinoids, methadone, and benzodiazepines will be assessed by urine drug screen measured at baseline, throughout detoxification, and at follow-up. Treatment retention will be calculated as the number of days each patient received his/her detoxification medication. The patient's status in the study will be tracked with a Study discharge report (SDR). The dispensing of ancillary medications will be tallied and grouped according to symptomology (several medications are permitted for treating anxiety, insomnia, nausea, etc.) and day during detoxification. Withdrawal symptoms will be assessed using the clinical opiate withdrawal scale (COWS), the adjective rating scale for withdrawal (ARSW), and visual analog scales (VAS) during detoxification and at follow-up (COWS and ARSW only). Additional measures of overall treatment effect will include a

shortened version of the Addiction Severity Index (ASI Lite), a client satisfaction questionnaire (CSQ), and SF-36 Health-related Quality of Life questionnaire administered at baseline and all follow-ups.

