8.0 STUDY DESIGN

A randomized, open-label, parallel groups study design will be used. After screening and baseline assessments, patients will be stratified for gender and randomly assigned in a 2:1 ratio to either a BUP/NX or clonidine 13-day detoxification. Patients will initiate detoxification in the inpatient setting and, as necessary, will continue detoxification as outpatients for the full 13 days. This typically ranges from 5 to 13 days of inpatient detoxification. After the 13 day detoxification, patients will be assessed for outcome measures including relapse and withdrawal symptoms at follow-up visits occurring 1, 3, and 6 months after starting detoxification. Counseling procedures in existence at each CTP will be used throughout the study. Self-help detoxification handbooks will be distributed to all study participants.

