10.0 INVESTIGATIONAL AGENTS

BUP/NX-combination:

Buprenorphine 2 mg and naloxone 0.5 mg or buprenorphine 8 mg and naloxone 2 mg sublingual tablets are manufactured by Reckitt and Colman Products (Hull, UK) and will be supplied through the National Institute on Drug Abuse and Research Triangle Institute.

Clonidine:

Clonidine (CATAPRES[®]- clonidine hydrochloride USP) is commercially available and is manufactured by Boehringer Ingelheim Pharmaceuticals, Inc., Ridgefield, CT. The clonidine to be used for this study is a 0.1 mg tablet for oral dosing and a transdermal therapeutic system (CATAPRES-TTS[®] - 1, 0.1 mg per day, for one week).

Ancillary Medications:

Ancillary medications used to treat opiate withdrawal side effects are commercially available and include:

Over the counter medications:

acetaminophen 650 mg

ibuprofen 200 mg loperimide 2 mg diphenhydramine 25 mg

Prescription medications:

oxazepam, tablets or capsules 15 mg and 30 mg
lorazepam, tablets 0.5 mg, 1 mg, and 2 mg
phenobarbital tablets, 15, 16 and 30 mg, capsules 16 mg
hydroxyzine hydrochloride tablets, 50 mg
methocarbamol tablets, 500 mg and 750 mg
trimethobenzamide capsules, 250 mg or 100/200 mg suppositories

Donnatal tablets or capsules – atropine sulfate 0.0194 mg, scoplamine hydrobromide
0.0065 mg, hyosyamine hydrobromide or sulfate 0.1037 mg, and phenobarbital 16
mg
zolpidem tartrate tablet, 5 and 10 mg
trazadone hydrochloride tablets 50 mg, 100 mg, 150 mg and 300 mg
doxepin hydrochloride tablets, 50 mg

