10.1 Dispensing Investigational Agents

Investigational agents will be dispensed daily according to the appropriate study arm while patients are in the inpatient setting. If patients are released for outpatient detoxification, investigational agents will continue to be dispensed in accordance with the inpatient procedures. Investigational agents will be prescribed, dispensed or administered (furnished) by an individual legally qualified to do so in accordance with state regulations. Patients receiving BUP/NX will be instructed to hold the tablet(s) under their tongue until dissolved. Dissolution of tablets will be monitored as clinically warranted by a nurse, physician or pharmacist at each CTP. Patients receiving oral clonidine will be instructed to swallow all pills and/or to leave their clonidine patch in place until replaced by the nurse, physician, or pharmacist at the study site.

For both in- and outpatient settings, it is recommended that patients be observed for at least several hours on the first day of treatment following the administration of bup/nx or clonidine until vital signs are stable.

Additionally, as clinically indicated, outpatients should not be allowed to drive home by themselves on the first (and sometimes second) day of bup/nx or clonidine treatment.

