If systolic B.P. is ≥ 100 mm Hg and pulse ≥ 56 bpm, give 0.1 mg oral clonidine test dose (0.05 mg for patients weighing less than 110 lbs,-0.2 mg for patients over 200 lbs). Check B.P. for orthostatic changes after 1 hour. The medical personnel should take B.P. after the patient is sitting for at least 3 minutes, and again after standing for 1 minute (note systolic B.P. and pulse). If systolic B.P. is ≥ 90 mm Hg and the pulse rate is ≥ 50 beats/min, put patient on a schedule of 0.1 mg clonidine q 4-6 hrs but do not exceed 0.6 mg for the first 24 hrs. If the systolic B.P. on recheck is < 90 mg Hg or the pulse rate is < 50 beats/min, instruct the patient to lie down and recheck the vital signs every hour until they return to normal (systolic B.P. ≥ 90 mm Hg and pulse rate is ≥ 50 beats/min). If the patient has symptomatic hypotension or bradycardia (i.e. syncope, dizziness, or chest pain) contact the physician and initiate the appropriate treatment. Treatment may include placing the patient in a recumbent position and beginning hydration with IV fluids.

Check the vital signs before each scheduled dose of clonidine. Skip the dose of clonidine if the systolic B.P. is < 90 mg Hg or the pulse rate is < 50 beats/min. Monitor for symptomatic hypotension, and adjust the dose if necessary. Drowsiness and orthostatic hypotension are common adverse effects of clonidine, requiring that the B.P. be monitored daily; however, these problems usually are not significant. Higher doses generally are needed for management of withdrawal than for treatment of hypertension.

Assuming that the patient tolerates clonidine well on the first day, apply clonidine patches in clinic according to the following weight schedule using TTS-1 patches:

| Weight | Clon | idine Patc |
|-------------|------|------------|
| < 110 lbs | 1-3 | TTS-1 |
| 110-200 lbs | 2-4 | TTS-1 |
| > 200 lbs | 2-6 | TTS-1 |

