The clonidine patch is a 0.2 mm square that is applied in the same manner as a self-adhesive bandage. It is available in three sizes: 3.5, 7.0, and 10.5 cm². In a 24-hour period, these patches deliver an amount of clonidine equivalent to twice-daily dosing with 0.1, 0.2 or 0.3 mg of oral clonidine, respectively. Once the patch is placed on the epidermal surface, clonidine enters the circulatory system through the skin. A rate-limiting membrane within the patch governs the maximum amount absorbed. The patch supplies clonidine for up to 7 days. Only one strength will be used (0.1). Multiple patches can be placed on the patient's upper body, and removed if clinically indicated. (TIP series, number 19 reference).

Day 2:

It takes 2 days for the clonidine patches to achieve a maximum blood concentration; therefore, oral clonidine usually needs to be continued on Day 2. Therefore, oral clonidine may be administered on day 2 as clinically indicated, depending on vital signs and opiate withdrawal symptoms. The clonidine dose may be increased to either 0.2 mg q

6 hrs or 0.1 mg q 3 hrs (but not to exceed 0.8 mg qd) as long as the vital signs sitting and standing are normal. Apply caution, observation and same withholding rules as in Day 1.

Days 3-6

The patch(es) given on Day 1 will provide sustained blood levels of clonidine for up to 7 days. However, if the patient does not tolerate the patches (i.e., they have a rash or persistent hypotension), the patch(es) should be discontinued and oral clonidine administered in its place in doses similar to that given on Day 2, but with adjustments as clinically indicated, through Day 7. Vital signs (sitting and standing) will be checked on every scheduled clinic visit or as instructed by the treating physician.

Day 7

On Day 7, remove all clonidine patches. Evaluate the patient's tolerance of clonidine, vital signs sitting and standing, opiate use during the detoxification, and symptoms of opiate withdrawal to decide whether or not to replace the patches or continue with oral clonidine. A common course is to reduce the dose by one-half for the second week.

Days 8-13

Continue to monitor vital signs for any changes of B.P. and pulse. Discontinue clonidine administration and remove any remaining patches by Day 13.

Day 14

Monitor vital signs for any rebound elevation of B.P.

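### The synopsis ties the repeated day-1 oral clonidine dose to weight; section 11.5.2 ties only the test dose to weight, then schedules a flat 0.1 mg

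*Protocol*

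**What the plan says.** Protocol section 3.0 (Synopsis, Study Interventions) describes day 1 as "oral clonidine (0.05 to 0.1 mg depending upon weight) every 4 to 6 hours for 24 hours not to exceed 0.6 mg". The weight range is attached to the dose repeated every 4 to 6 hours. No weight is named and no test dose appears.

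Protocol section 11.5.2 (Clonidine, Day 1) gives two steps. If entry blood pressure and pulse are acceptable, staff "give 0.1 mg oral clonidine test dose (0.05 mg for patients weighing less than 110 lbs,-0.2 mg for patients over 200 lbs". After a 1-hour recheck, a patient with systolic pressure of at least 90 mm Hg and pulse of at least 50 goes on: "put patient on a schedule of 0.1 mg clonidine q 4-6 hrs but do not exceed 0.6 mg for the first 24 hrs". This second step has no weight tier.

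On day 2 the texts agree that weight plays no part in the oral dose. In section 11.5.2, "The clonidine dose may be increased to either 0.2 mg q" 6 hours, or to 0.1 mg every 3 hours, up to 0.8 mg. The synopsis gives the same two doses and the same limit.

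**The concern.** Section 11.5.2 and the synopsis are both current text, and nothing in the Protocol says which one governs. A site treating a light patient can find 0.05 mg in one place and 0.1 mg in the other, at that patient's first exposure to clonidine.

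The section 11.5.2 rule also sits oddly with its own test dose. The middle weight group is tested at 0.1 mg and scheduled at 0.1 mg. The heaviest group is tested at 0.2 mg and scheduled at 0.1 mg. Only the group under 110 lbs is scheduled at more than the dose whose effect was checked. Such patients can be enrolled: section 9.1 admits patients from age 15 and sets no minimum weight.

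What is at stake is consistent and cautious first-day dosing in a small part of the clonidine arm. No estimate or test depends on it.

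**Working it through.** **Inputs.** Synopsis: 0.05 to 0.1 mg by weight, every 4 to 6 hours, ceiling 0.6 mg. Section 11.5.2: test dose 0.05 mg under 110 lbs, 0.1 mg standard, 0.2 mg over 200 lbs; then 0.1 mg every 4 to 6 hours; ceiling 0.6 mg.

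**The plan's own figure.** Ceiling = dose × 24 / interval = 0.1 × 24/4 = 0.6 mg. It reproduces and is the same in both texts. At 0.05 mg the most that scheduled dosing can reach is 0.05 × 24/4 = 0.30 mg. The ceiling therefore never binds at that dose and cannot show which rule is meant.

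**Scheduled dose against tested dose, section 11.5.2.**

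| Weight | Test dose | Scheduled dose | Ratio |
|---|---|---|---|
| under 110 lbs | 0.05 mg | 0.1 mg | 2 |
| 110 to 200 lbs | 0.1 mg | 0.1 mg | 1 |
| over 200 lbs | 0.2 mg | 0.1 mg | 0.5 |

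**Scheduled dose between texts, under 110 lbs.** Assumption: the synopsis means its 0.05 mg for this group. Then 0.1 / 0.05 = 2.

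**Day-1 totals under 110 lbs.** Read literally, the synopsis has no test dose: 4 × 0.05 = 0.20 mg (every 6 hours) to 6 × 0.05 = 0.30 mg (every 4 hours). Setting that beside section 11.5.2 would count a test dose on one side only. For a like-for-like comparison, the 0.05 mg test dose is added to both. Section 11.5.2 does not say how soon the first scheduled dose follows the test dose, so the range from 1 hour to one full interval is shown.

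| Interval, first scheduled dose | Scheduled at 0.05 mg | Scheduled at 0.1 mg | Difference |
|---|---|---|---|
| 6 h, at hour 6 | 0.05 + 3 × 0.05 = 0.20 | 0.05 + 3 × 0.1 = 0.35 | 0.15 |
| 6 h, at hour 1 | 0.05 + 4 × 0.05 = 0.25 | 0.05 + 4 × 0.1 = 0.45 | 0.20 |
| 4 h, at hour 4 | 0.05 + 5 × 0.05 = 0.30 | 0.05 + 5 × 0.1 = 0.55 | 0.25 |
| 4 h, at hour 1 | 0.05 + 6 × 0.05 = 0.35 | 0.05 + 6 × 0.1 = 0.65, held to 0.60 | 0.25 |

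The totals are 0.20 to 0.35 mg against 0.35 to 0.60 mg. Case by case the ratios are 1.75, 1.80, 1.83 and 1.71. The Protocol gives no weight distribution, so the number of patients affected cannot be estimated.

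**The case against.** The best defence is that the synopsis cannot be dosed from. It has no cut-off, no test dose and no hold rule, so staff must use section 11.5.2, which gives one clear sequence. On this view the synopsis only runs the test-dose tiers and the schedule together. Part of that stands: section 11.5.2 is the likelier working text. But a plain condensation of the tiers would run from 0.05 to 0.2 mg. The synopsis range stops at 0.1 mg and is attached to the repeated dose. If section 11.5.2 does govern, the synopsis misstates the regimen and still needs correcting.

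The synopsis also says the clonidine dose will be adjusted for weight, tolerance and blood pressure, and section 11.5.2 allows adjustment. This softens the effect but does not choose a rule: the synopsis gives no tier, and section 11.5.2 links adjustment to symptomatic hypotension.

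The safeguards are real. Entry requires systolic pressure of at least 100 mm Hg and pulse of at least 56 bpm (section 9.1). "Patients will initiate detoxification in the inpatient setting" (section 8.0), and "it is recommended that patients be observed for at least several hours on the first day of treatment" (section 10.1). Vital signs precede every dose, with a hold below 90 mm Hg or 50 beats/min. Of drowsiness and orthostatic hypotension, section 11.5.2 says they are common; "however, these problems usually are not significant".

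A reader might infer that the synopsis expressly sets 0.05 mg for patients under 110 lbs. It names no weight; the cut-off comes from section 11.5.2, the only place that ties 0.05 mg to a weight. A reader might also infer that a new step-up schedule is needed. Neither text contains one, and section 11.5.2 says the clonidine regimen was built to match practice at participating sites. The Protocol supports reconciling its own two rules, not adding a third.

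**Conclusion.** The inconsistency is real and the text is wrong as written. The synopsis makes the repeated day-1 oral dose weight-dependent, section 11.5.2 does not, and no text settles it. The factor of 2 in the scheduled dose rests on the inference that the synopsis means 0.05 mg for patients under 110 lbs. That scheduled dosing in section 11.5.2 is twice the tested dose for this group needs no such inference.

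The conflict is confined to oral dosing on day 1. A reader might take it for a serious hazard or a threat to the trial's conclusions. The Protocol does not support that: the ceiling is shared, the hold rules apply to every dose, treatment starts in an inpatient setting, and neither the primary analysis nor the sample size uses the dose. It is a minor safety and consistency correction.

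**What to change.** State one rule in both places, using tiers the Protocol already has. For section 11.5.2, Day 1, suggested wording: *Scheduled oral dose 0.1 mg, or 0.05 mg if body weight is below 110 lbs, at intervals of 4 to 6 hours; adjust for tolerance and vital signs; 24-hour maximum 0.6 mg.* In the synopsis, add the weight-based test dose and the 110 lb cut-off. If the sponsor intends the flat 0.1 mg after the test dose, leave section 11.5.2 alone and correct the synopsis to say so.

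The cost is one amendment to one or two dosing texts, with no change to visits, sample size or analysis. No new supply is needed: "The clonidine to be used for this study is a 0.1 mg tablet for oral dosing", so 0.05 mg is half a tablet, which the test dose under 110 lbs already requires.

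The downside of the first option is lower day-1 oral exposure in light patients: 0.15 to 0.25 mg less in the cases above if no dose is adjusted. A move to 0.2 mg on day 2 would then be fourfold from 0.05 mg rather than twofold from 0.1 mg. In section 11.5.2 that increase is optional and requires normal sitting and standing vital signs, and the day-1 adjustment clause lets staff raise the dose sooner. The second option avoids this cost but keeps a scheduled dose twice the tested one for the lightest patients.
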